8. RESEARCH METHODS

8.1. Study Design

This is a prospective, non-interventional (NI), multicenter study being conducted in the US and CAN. The primary goal is to understand palbociclib prescribing and treatment patterns for patients with ABC being treated in routine clinical practice in the US and CAN.

Approximately 1,500 subjects will be enrolled across approximately 100 sites in the US and 10 sites in CAN. Study duration will consist of observation of patients on palbociclib treatment and approximately 3 years of follow-up post each patient's end of treatment with palbociclib, or until patient withdrawal from the study or death.

Participation in this study is not intended to change the routine treatment patients receive, as determined by their prescribing physicians; all treatment decisions, type and timing of disease monitoring are at the discretion of treating physician and patient.

Assessments include patient questionnaires and quality of life (EORTC QLQ-C30, G8 Screening Tool, ADL), site questionnaires, physician MBC treatment selection survey, and **CCI** [REDACTED], as detailed in Section 8.3 and Section 8.4.

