Real-world tumor response (complete response, partial response, stable disease, progressive disease) is determined by physician based on imaging, biopsies, biomarkers, and/or clinical judgment. Response as assessed by Response Evaluation Criteria in Solid Tumors (RECIST) criteria may not be available for all patients. rwTR will be derived as the best tumor response recorded from the palbociclib combination treatment start date until the first documentation of progressive disease. Only response assessments recorded on or before the start date of next subsequent line of treatment will be considered. The proportion of patients with a best response of complete response, partial response, stable disease, and progressive disease will be calculated and reported. Real-world response rate is defined as the proportion of patients with a best tumor response of complete response or partial response. Best tumor response, clinical benefit, and study end date are defined in Appendix 1 Data Derivation Details.

rwPFS will be estimated by LOT in the ABC/MBC setting. rwPFS is defined as time (months) from initiation of the palbociclib combination treatment to the earliest of clinician-documented progression or death due to any cause, whichever occurs first. Patients absent of the above events will be censored at the last date of response assessment without progressive disease.

OS will be estimated by LOT in the ABC/MBC setting. OS is defined as time (months) from initiation of the palbociclib combination treatment to date of death due to any cause. Patients do not have a documented death will be censored at last available visit date known to be alive.

Follow-up time will be calculated as time (months) from initiation of the palbociclib combination treatment to date of death or last available visit date. Median follow-up time and range (minimum, maximum) will be provided overall and by LOT.

Time-to-event outcomes (i.e., rwPFS, OS) will be analyzed using the Kaplan-Meier method and estimated survival curves will be displayed when appropriate. The number of patients at risk over time will be presented. A summary table will include number of patients with events, number of patients censored, and Kaplan-Meier quartiles (when estimable) accompanied by two-sided 95% confidence intervals (CIs). Based on the Kaplan-Meier life table, Survival function estimates at the specific time points (eg, 6, 12, 18, 24, 30 and 36 months) will also be reported along with two-sided 95% CIs.

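### Median follow-up is taken from time to death or last visit, so it understates potential follow-up for OS, most where mortality is highest, and is the wrong clock for rwPFS

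*SAP*

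**What the plan says.** All the relevant text is in SAP section 8, Clinical Outcomes.

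- Follow-up: "Follow-up time will be calculated as time (months) from initiation of the palbociclib combination treatment to date of death or last available visit date". It is summarised as follows: "Median follow-up time and range (minimum, maximum) will be provided overall and by LOT". No estimator is named there or in Appendix 1.
- OS: "OS is defined as time (months) from initiation of the palbociclib combination treatment to date of death due to any cause". Censoring: "Patients do not have a documented death will be censored at last available visit date known to be alive".
- rwPFS censoring: "Patients absent of the above events will be censored at the last date of response assessment without progressive disease".
- Other outputs that bear on how well the curves are supported: "The number of patients at risk over time will be presented", and "A summary table will include number of patients with events, number of patients censored, and Kaplan-Meier quartiles (when estimable") with 95% CIs. Survival estimates at fixed times, with 36 months as the latest example, are also planned.

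Protocol section 8.1 sets the observation period as time on palbociclib plus "approximately 3 years of follow-up post each" patient's end of treatment, unless withdrawal or death comes first.

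**The concern.** Follow-up time and OS share the same origin, the same death date and in substance the same last-visit date. The follow-up variable is therefore the OS time without its event indicator. A patient who dies at month 10 contributes 10 months of follow-up, although that patient's survival is completely known and the study might have observed them for 50 months. The median then mixes how long patients lived with how long the study could watch them.

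Readers use median follow-up to judge whether a curve has been observed long enough, and to check that strata were observed alike. The SAP reports it for the same line-of-therapy strata in which OS is reported, so a difference in survival can appear as a difference in follow-up. Section 4 of the SAP also plans several interim analyses timed partly to congress deadlines, so the figure may recur in short reports.

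**Working it through.** The documents state no median follow-up, so there is no figure to reproduce.

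**Inputs from the documents.** Data collection runs from 16 Dec 2016 to 16 Dec 2021, a 60-month window (Protocol section 5). Observation ends about 36 months after palbociclib stops (Protocol section 8.1). Median PFS values of 24.8 and 9.2 months (Protocol section 6.2) are used only for scale.

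**Assumptions, not in the documents.** Accrual pattern, loss to follow-up, median OS, treatment duration, assessment interval, and exponential times.

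**1. Direction for OS.** Let S(t) be the probability of being alive at t and G(t) the probability that observation would still be open at t. If the two are independent:

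- the plain median m of min(death, last visit) solves S(m) × G(m) = 0.5;
- the reverse Kaplan-Meier median c (deaths treated as censored) solves G(c) = 0.5.

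Since S(t) ≤ 1, m cannot exceed c, and it falls as mortality rises.

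**2. Worked case.** Take uniform accrual over 30 months, a cut at 60 months and no loss. Then G(t) = 1 up to month 30 and (60 − t)/30 after it, so c = 45. With S(t) = 2^(−t/median OS):

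| Median OS | m | Check S × G | c − m |
|---|---|---|---|
| 24 | 24.0 | 0.500 × 1.000 = 0.500 | 21.0 |
| 36 | 32.1 | 0.539 × 0.930 = 0.501 | 12.9 |
| 48 | 35.1 | 0.602 × 0.830 = 0.500 | 9.9 |

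**3. Wider grid.** Simulation covered 36 combinations: three ranges of potential follow-up, loss of 0, 5 or 10% a year, and median OS of 24 to 60 months. The plain median was lower in all 36.

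| Potential follow-up (months) | Range of c − m |
|---|---|
| 12–60 | 6.8 to 17.1 |
| 24–60 | 7.3 to 17.9 |
| 36–60 | 7.1 to 24.5 |

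For example, with 24–60 months and 5% a year loss, median OS of 24, 36, 48 and 60 gives m = 20.9, 26.5, 29.0 and 30.7, against c of about 38.8 throughout.

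**4. Adding the 3-year limit.** In the case of step 2, G(t) beyond month 36 is also multiplied by 2^(−(t − 36)/median treatment duration). With 24.8 months and no loss, c = 42.2: (17.8/30) × 2^(−6.2/24.8) = 0.593 × 0.841 = 0.499.

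| Median treatment | Loss/year | c | m for OS 24 / 36 / 48 | c − m |
|---|---|---|---|---|
| 9.2 | 0 | 39.9 | 24.0 / 32.1 / 35.1 | 15.9 / 7.8 / 4.8 |
| 24.8 | 0 | 42.2 | 24.0 / 32.1 / 35.1 | 18.2 / 10.1 / 7.1 |
| 9.2 | 5% | 38.6 | 20.9 / 29.5 / 32.5 | 17.7 / 9.1 / 6.1 |
| 24.8 | 5% | 40.1 | 20.9 / 29.5 / 32.5 | 19.2 / 10.6 / 7.6 |

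**5. By line of therapy.** Under identical observation (step 2), strata with median OS of 24 and 48 months show 24.0 and 35.1 months of follow-up. This 11.1-month difference is due to survival alone. With the limit, no loss, and treatment medians of 9.2 and 24.8 months respectively, potential follow-up does differ, but by 42.2 − 39.9 = 2.3 months, while the plain medians still differ by 11.1.

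**6. rwPFS.** Simulation used 24–60 months of potential follow-up, 5% a year loss and assessments every 3 months. Median survival after progression was 48 − 24.8 = 23.2 or 24 − 9.2 = 14.8 months. A share of patients each year stops being assessed while still attending. The last two columns differ in whether a death after assessments have stopped counts as an rwPFS event; under the SAP definition it does.

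| Median PFS | SAP median | Stop assessment/year | Reverse KM, such deaths not counted | Reverse KM, counted |
|---|---|---|---|---|
| 24.8 | about 32.6 | 0% | 36.0 | 36.0 |
| | | 15% | 27.0 | 30.0 |
| | | 30% | 18.0 | 24.0 |
| 9.2 | about 25 | 0% | 36.0 | 36.0 |
| | | 15% | 27.0 | 36.0 |
| | | 30% | 18.0 | 39.0 |

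In the first block the SAP figure is too low when assessments continue and too high when they lapse. Lapses are plausible: SAP Table 1 limits data entry after palbociclib to the start of each new regimen and the end of study. In the second block, counting late deaths makes the reverse Kaplan-Meier figure rise as assessments stop sooner. That is an artefact, because survivors are censored at the last assessment while deaths count whenever they occur.

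**The case against.** - **The SAP states exactly what it computes.** Time to death or last visit is a legitimate description of time on study, and it is an underestimate only if read as potential follow-up. This stands, and is why relabelling is part of the fix. The plain median is also inferred from the request for a median with minimum and maximum; it is the natural reading, not an explicit instruction.
- **Maturity is shown elsewhere.** A reader might infer that the 36-month estimates are compromised. The documents do not support that: events, censored counts, numbers at risk and confidence intervals do not use this variable. For OS the error also makes the data look less followed, not more.
- **rwPFS.** A reader might infer that rwPFS follow-up is understated too. Its censoring date is different, and step 6 shows no fixed direction.
- **The 45-month benchmark.** It ignores loss and the 3-year limit. With both, the reverse Kaplan-Meier median is about 39 to 40 months. The gap shrinks but remains.
- **Lines of therapy may truly differ.** Patients treated for less time leave observation sooner, so not every difference between strata is an artefact. If treatment duration and survival are correlated, reverse Kaplan-Meier is itself distorted: with a correlation of 0.5 it exceeded true median potential follow-up by about 1 to 2 months. This stands as a caveat, but it is smaller than the gaps in step 4.

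**Conclusion.** The point holds as a defect in one descriptive summary. For OS, a plain median of this variable understates potential follow-up, and the shortfall grows with mortality, so the by-line comparison can mislead. With independent censoring that direction is general; the size is not. It is roughly 7 to 21 months in most runs, 6.8 to 24.5 over the grid without the 3-year limit and 4.8 to 19.2 with it. These sizes rest on assumed accrual, loss, median OS, treatment duration and exponential times. For rwPFS the conclusion is only that the clock is wrong and the error may go either way. No estimate, interval or event count in the plan changes.

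**What to change.** In SAP section 8, Clinical Outcomes:

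1. Rename the present quantity *observed time on study* and keep its median and range.
2. Add median follow-up for OS by reverse Kaplan-Meier with 95% CI, overall and by line of therapy, using the OS times with the event indicator flipped.
3. Add a separate reverse Kaplan-Meier median for rwPFS, using its own censoring date. Because of the artefact in step 6, show beside it the interval from last response assessment to last visit in patients censored for rwPFS.
4. Add a note that observation ends about 3 years after palbociclib stops, so censoring may depend on prognosis, the reverse Kaplan-Meier figures are approximate, and lines of therapy may differ genuinely in potential follow-up.

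No new data are needed and no planned output is lost. The cost is a few sentences in the SAP and one or two extra procedure calls.

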8.8.1 Adverse Events

All safety analyses will be completed following Pfizer safety analysis standards, including descriptive statistics on all safety endpoints for the FAS. AEs will be monitored throughout the study duration. If the type and/or number of AEs warrants further examination, interim analyses will be conducted to determine whether those experiencing AEs are systematically different from other study participants. If the percentage of patients withdrawing from the study exceeds 25%, interim analyses will be conducted to examine whether systematic differences exist between those withdrawing from the study and those that continue with palbociclib treatment. Descriptive statistics comparing women and men who complete follow-up with those who withdraw from the study will also be completed to determine whether there are any systematic (demographic, clinical) differences between these such defined groups.

Descriptive statistics will be presented for all AEs and will be examined by AE grade. The incidence of all-cause and treatment-related AEs and SAEs separately will be reported. Specifically, a summary of incidence will be presented for the following variables:

- Patients evaluable for AEs
- Number of AEs
- Patients with AEs

PFIZER CONFIDENTIAL

- Patients with SAEs
- Number of SAEs
- Patients with Grade 3 or 4 AEs
- Patients with Grade 5 AEs
- Patients permanently discontinued study associated with AEs
- Patients permanently discontinued study associated with SAEs
- Patients permanently discontinued treatment associated with AEs
- Patients permanently discontinued treatment associated with SAEs
- Patients temporarily discontinued treatment associated with AEs
- Patients temporarily discontinued treatment associated with SAEs
- Patients with dose reduction associated with AEs
- Patients with dose reduction associated with SAEs
- Deaths

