A phase 3 study, PALOMA-2 (Finn et al, 2016), was conducted with 666 post-menopausal women without prior systemic therapy for ER+/HER2– ABC. Patients were randomized to a 2:1 ratio to receive palbociclib + letrozole or placebo + letrozole. The median PFS was 24.8 months with palbociclib + letrozole and 14.5 months with placebo + letrozole (HR=0.58; 95% confidence interval [CI] 0.46, 0.72, $P<0.000001$). Common adverse events (AEs; all grades) with palbociclib + letrozole vs placebo + letrozole were neutropenia (75% vs 5%), fatigue (41% vs 23%), nausea (25% vs 13%), arthralgia (33.3% vs 33.8%), and alopecia (32.9% vs 15.8%). Grade 3/4 neutropenia occurred in 54% of patients; other AEs were of Grade 1 severity. Febrile neutropenia was seen only with palbociclib + letrozole (2.5%). Permanent discontinuation due to AEs occurred in 9.7% of patients receiving palbociclib + letrozole vs 5.9% receiving placebo + letrozole. PALOMA-2 confirmed the significant clinical benefit and safety of palbociclib + letrozole in ER+/HER2– ABC patients who had not received prior systemic therapy for their advanced disease (Finn et al, 2016).

Another phase 3 study, PALOMA-3, was conducted with 521 patients with advanced HR+/HER2– patients that had relapsed or progressed during prior endocrine therapy (Turner et al, 2015). Patients were randomized to a 2:1 ratio to receive palbociclib + fulvestrant or placebo + fulvestrant. The median PFS was 9.2 months (95% CI, 7.5, upper limit not estimable) with palbociclib + fulvestrant and 3.8 months (95% CI 3.5, 5.5) with placebo + fulvestrant (HR for disease progression or death, 0.42; 95% CI 0.32, 0.56; $P<0.001$). The most common grade 3 or 4 AEs in the palbociclib+fulvestrant group were neutropenia (62.0%, vs. 0.6% in the placebo + fulvestrant group), leukopenia (25.2% vs. 0.6%), anemia (2.6% vs. 1.7%), thrombocytopenia (2.3% vs. 0%), and fatigue (2.0% vs. 1.2%). Febrile neutropenia was reported in 0.6% of patients in each treatment group. The rate of discontinuation due to AEs was 2.6% vs. 1.7% (Turner et al, 2015).

Estrogen receptor-positive breast cancer is biologically heterogeneous. Although palbociclib clinical trial results are very promising, it is also recognized that not all patients may respond to palbociclib treatment, and palbociclib treatment does come with mechanism based toxicities. **CCI**

[REDACTED]

[REDACTED]

[REDACTED]

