4 INTERIM ANALYSES

The study will consist of several interim analyses and a final analysis. The frequency and timing of the interim analyses will be driven by the observations and events available and also strategic medical interest (e.g., congress research submission deadlines). Each interim analysis will include data on baseline characteristics for patients enrolled in the study as well as longitudinal endpoints for patients with sufficient follow-up. Interim analyses will include summaries of patient, physician, and site characteristics. The specific measures (e.g., changes in patient-reported outcomes score, time-to-event analyses) presented for each interim analysis will be determined by Pfizer and analysis contributors based on the longitudinal data available at the time each interim dataset is released. At the time of each interim analysis, summaries related to treatment regimen, prescribing patterns, and dosing may be conducted as needed for abstracts and manuscripts provided sample sizes are sufficient for estimation.

PFIZER CONFIDENTIAL

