8 STATISTICAL ANALYSIS

This study has a convenience sample; thus, results may not be generalizable to the entire population with the disease. Due to the study's exploratory nature, study measures will be summarized descriptively. Furthermore, any p value reporting should be placed in a descriptive framework for hypothesis generation and any such inferential analysis is intended to guide further research.

All analyses will be conducted using SAS® version 9.4 or higher.

The intention is to analyze all available data. In the advent that COVID may cause gaps in subject data or require adjustments to statistical methodologies, our intent is to address such issues if or as needed. Both ICON and Pfizer have internal guidances and recommendations on file to assist with decision-making with regards to COVID-related data issues and these will be consulted if or as needed.

GENERAL METHODS

For continuous variables, means, standard deviations (SD), medians, minimums, maximums, and missing will be reported. For discrete variables, frequencies and percentages will be reported. Missing or unknown categories for each variable also will be presented. Percentages will be calculated excluding missing or unknown values. 95% Confidence Intervals (CI) are two-sided.

All summaries will be performed for all patients in the corresponding analysis set and by treatment combination defined at study entry within the corresponding analysis set:

- Palbociclib + Letrozole or Anastrozole
- Palbociclib + Fulvestrant
- Palbociclib + Exemestane
- Other

The baseline record is defined as the last observed measurement prior to palbociclib administration. Change from baseline is defined as the post-baseline value minus the baseline value.

Time in days between two dates will be calculated using the formula most recent date minus earlier date plus 1. For time in months, the same formula for days will be applied but then divided by 30.4. For time in years, the same formula for days will be applied but then divided by 365.25.

Variable definitions are found in Appendix 1 Data Derivation Details.

DISPOSITION OF SUBJECTS

A subject disposition summary will be reported. Subjects' study completion date and reason for premature termination will be reported in listing format. Number of subjects with initial diagnosis and with recurrent diagnosis will be reported in table and listing format.

DEMOGRAPHIC AND BASELINE CLINICAL CHARACTERISTICS

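### AE and SAE incidence is tabulated by palbociclib partner as crude percentages with no allowance for time at risk, although AE observation lengthens with time on drug

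*SAP*

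**What the plan says.** SAP 8.8.1 fixes the safety measure: "The incidence of all-cause and treatment-related AEs and SAEs separately will be reported". Its rows are numbers of events and numbers of patients (any AE, SAE, Grade 3 or 4, Grade 5, discontinuation, dose reduction). The only denominator row is the number of patients evaluable for AEs.

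SAP section 8, General Methods, fixes the form: "For discrete variables, frequencies and percentages will be reported". It also fixes the split: "All summaries will be performed for all patients in the corresponding analysis set and by treatment combination defined at study entry", the groups being letrozole or anastrozole, fulvestrant, exemestane, and other.

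The documents state the end of AE collection in two ways. Footnote 8 of Table 1, in both protocol and SAP, ends it 28 days after the last palbociclib dose. Protocol section 10, Reporting period, runs it to the end of the observation period, which must include at least 28 days after the last dose.

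On interims, SAP section 4 says "The frequency and timing of the interim analyses will be driven by the observations and events available and also strategic medical interest". It leaves the measures to be chosen each time and does not name AE tables.

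Other endpoints do get a time element. rwPFS and OS have Kaplan-Meier curves with numbers at risk and fixed-time estimates (SAP Clinical Outcomes), and laboratory values are shown by cycle (SAP 8.8.2). Length of palbociclib treatment is summarised under Study Drug Exposure but is not linked to the AE tables.

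**The concern.** A crude percentage of patients with an event depends on the risk per month and on the number of months observed. Under footnote 8 the months observed follow time on drug. If one partner group stays on palbociclib longer, its SAE percentage rises even when the monthly risk is the same, and side-by-side columns invite the reading that the partner is more toxic. The same mechanism affects the comparison in SAP 8.8.1 of patients with and without AEs, because longer-treated patients have more opportunity to enter the AE group. It would also affect any AE table produced at an early data cut. These figures are meant to describe real-world safety, and the SAP introduction quotes trial AE percentages that readers will set beside them.

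**Working it through.** The plan states no exposure time, AE rate or exposure ratio by partner, so there is no figure of its own to reproduce. What follows is an illustration under stated assumptions.

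**Inputs from the documents**
- Protocol 6.2: "The median PFS was 24.8 months with palbociclib + letrozole and 14.5 months with placebo + letrozole", in patients without prior systemic therapy for ABC.
- Protocol 6.2: "The median PFS was 9.2 months (95% CI, 7.5, upper limit not estimable) with palbociclib + fulvestrant", in patients who had relapsed or progressed on prior endocrine therapy.
- Tail after last dose: 28 days = 28/30.4 = 0.92 months, using the SAP's month length.
- Data collection runs from 16 December 2016 to 16 December 2021, so at most about 60 months per patient.

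**Assumptions**
- The two PFS medians stand in for time on drug.
- Time on drug is exponential. As a rough check, the ratios of quoted medians, 14.5/24.8 = 0.585 and 3.8/9.2 = 0.413, agree with the quoted hazard ratios of 0.58 and 0.42.
- Both groups have the same constant first-event hazard h per month. I use 0.005, 0.01 and 0.02 for SAEs, since the documents give no rate.

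**Exposure.** The ratio of medians is 24.8/9.2 = 2.70, but this is reached only with unlimited follow-up. Mean time on drug up to follow-up T is (1 − exp(−mT))/m, with m = ln 2/median (0.0279 and 0.0753). The ratio is 1.14 at 6 months, 1.29 at 12, 1.58 at 24, 1.83 at 36 and 2.22 at 60.

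**Crude percentage.** Observation is the shorter of time on drug plus g = 0.92 months and T. Then

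P(event) = 1 − [exp(−hg) · m/(m+h) · (1 − exp(−(m+h)(T−g))) + exp(−m(T−g)) · exp(−hT)].

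| h per month | T = 12 | T = 24 | T = 60 |
|---|---|---|---|
| 0.005 | 5.1% v 4.1% (1.24) | 8.5% v 5.7% (1.50) | 13.4% v 6.6% (2.03) |
| 0.01 | 9.9% v 8.0% (1.23) | 16.2% v 10.9% (1.48) | 24.3% v 12.5% (1.95) |
| 0.02 | 18.7% v 15.3% (1.23) | 29.2% v 20.1% (1.45) | 40.4% v 22.3% (1.81) |

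The true hazard ratio is 1.0 in every cell. For a frequent event with h = 0.5 per month, the percentages at 24 months are 96.7% v 91.7% (1.05).

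**Mixed lines.** Suppose 80-90% of the letrozole/anastrozole group and 30-50% of the fulvestrant group are first-line (an assumption), with the two medians applying by line. At h = 0.01 the crude ratio falls to 1.12-1.25 at 24 months and 1.19-1.44 at 60.

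**Data cut.** At h = 0.01 and a 24.8-month median, the percentage in one group is 5.5% at 6 months of potential follow-up, 16.2% at 24 and 20.1% at 36, with no change in risk.

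**End of AE reporting.** Using the medians, the ratio of observation windows is (24.8 + 0.92)/(9.2 + 0.92) = 2.54 under footnote 8. If reporting runs through about 36 months of post-treatment follow-up, as protocol section 10 allows, it is (24.8 + 36)/(9.2 + 36) = 1.35.

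**Would a simple rate per patient-month suffice?** Take identical front-loaded hazards, 0.3 per month for 2 months and 0.005 afterwards, over 36 months with no tail. Person-time per patient is (1 − exp(−2(0.3+m)))/(0.3+m) + exp(−2(0.3+m)) · (1 − exp(−34(0.005+m)))/(0.005+m), which gives 12.08 v 6.90 months. Weighting the two terms by their hazards gives 0.493 v 0.449 events. The rates are 4.1 v 6.5 per 100 patient-months, a spurious difference in the opposite direction. Fixed-time incidence avoids this.

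**The case against.** **The 2.7 ratio.** A reader might infer that the documents' medians imply a 2.7-fold difference in exposure between this study's partner groups. They do not. The medians are PFS, not time on drug, and come from two external trials in different lines of therapy. This study enrols any line with any partner, and nothing is quoted for exemestane or the other group. Likewise, crude ratios of 2.0 to 2.4 follow only from unlimited follow-up without the 28-day tail. This objection stands, so the medians serve only as an upper-end proxy.

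**Interims.** A reader might also infer that AE percentages will be shown at every interim. SAP section 4 names no AE tables and restricts longitudinal endpoints to patients with sufficient follow-up. The AE-triggered interim in SAP 8.8.1 is conditional and compares patient characteristics. The drift therefore applies to any AE table that is shown, not to a planned series.

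**Descriptive purpose.** The SAP places inference in a hypothesis-generating frame and says clinical endpoints will not be compared between regimens. No formal test is biased. But General Methods still requires safety summaries by partner, and a percentage over unequal observation misdescribes risk without any test.

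**Already covered.** Treatment length is summarised and, under General Methods, would also appear by partner, so a careful reader could see unequal exposure but could not adjust for it. SAP 8.8.1 also invokes sponsor safety standards. Their content is not in the documents, so they may or may not fill the gap.

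**Conclusion.** The concern holds in a limited form. SAP 8.8.1 and General Methods plan crude AE and SAE percentages by partner with no time-at-risk element, while footnote 8 ties AE observation to treatment length. If the quoted PFS medians approximate time on drug and the SAE hazard is constant and equal, the crude ratio is about 1.2 at 12 months of follow-up, 1.5 at 24 and 1.8 to 2.0 at 60; the last is an outer limit that only the earliest enrolled patients could reach. Mixed lines of therapy shrink it. Early, frequent events are hardly affected; SAEs, discontinuations and later events are. If AE reporting runs to the end of observation, the imbalance in observation time is smaller. The issue is misreading of descriptive tables, and it is worth correcting because the remedy is cheap.

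**What to change.** 1. Reconcile protocol section 10 (Reporting period) with footnote 8 of Table 1 in both documents on when AE reporting ends, since this sets the time at risk.
2. In SAP 8.8.1, mainly for SAEs, Grade 3 or higher AEs, and AE-related discontinuations and dose reductions, add cumulative incidence at fixed times on treatment (for example 3, 6 and 12 months), overall, by partner and by line of therapy. Censor at the end of AE observation or the data cut, and treat death as a competing event where relevant. Patients already on palbociclib at consent enter the risk set at consent (delayed entry). State that censoring assumes stopping is unrelated to later event risk.
3. Show median exposure, patient-time and data cut-off in every AE table, including any interim one.
4. Give first-event rates per 100 patient-months only as a supplement, noting that they assume a roughly constant hazard.
5. Base the comparison of patients with and without AEs on a fixed early window, among patients followed that long.

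The crude percentages stay. The cost is SAP text and a few more columns, using treatment and AE data already collected.
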